Method of subject assignment to study groups

The primary investigator will be the one to approach the potential participants for their informed consent. Among those who consented, They will be screened for eligibility, then randomized using a pre generated sequential list using an online application https://www.random.org/ either to group A (no antibiotic prophylaxis) and to group B (with antibiotic prophylaxis using 1g IV Cefoxitin).

Description of procedure/s for all study groups

Group A – Experimental Group

In the experimental group, patients will be given normal saline solution in a syringe, which is identical to syringes used to give antibiotics 1 hour prior to the procedure. Both solutions will be clear, which means neither patient or doctor will be aware of what was given as to avoid bias. Only the staff of the stone center will be aware of this. They will be instructed by the researcher or the consultant or research assistant to perform this one hour prior to the procedure just like giving prophylactic antibiotics.

Group B With Antibiotic Prophylaxis using Cefoxitin 2g IV

Patients will be given 2g IV of Cefoxitin 1 hour prior to the procedure.

After being given NSS or Cefoxitin, both groups will undergo transperineal prostate biopsy. Standard skin preparation will be done for both groups. Excessive hair is shaved off the perineum. The perineum is prepared using Betadine (10% povidone-iodine). The perineum is then prepped with betadine solution starting from the center of the perineum with 1 passage from inside to outside for 5 times Biopsy will then be performed. Biopsy procedure to be done is the standardized technique recommended by the American urologic Association, which involves a targeted (lesion centered) biopsy, followed by a systematic biopsy to get a representation of all parts of the prostate gland. After the procedure, the post biopsy site will be cleaned thoroughly using cutasept solution. The patient will then be awaken once the procedure is done, and will be sent to the recovery room for observation. Patients should void prior being discharged home. A temporary urinary catheter is placed if patients develop acute urinary retention. Patients will then be taught on the symptoms of UTI or sepsis and advised to seek medical attention if these occur.

Randomization and Blinding procedures

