Once the patient has given his signed consent, and patient is eligible to join the study, he will then be randomized into the experimental or control group using the online app https://www.random.org. The app generates a sequential list which prevents the investigator from learning allocation before a patient is registered into the study and from altering allocation afterwards, thus full concealment. Randomization will be performed by a research assistant not involved in the administration of treatments or data collection. The sequential list will be saved in a password protected file only accessible to the research assistant.. After a patient has been allocated, the group assignment will be permanent and unmodifiable. The randomization codes will be kept by the research assistant as well. Antibiotic or placebo will be administered by the stone center staff before the patient is put to sleep. The primary investigator will not be part of the biopsy procedure for blinding purposes.

Risks

One of the common side effects of prostate biopsy is infection. According to studies, 2% patients may experience mild disease not requiring hospitalization, and 1% may experience severe infections requiring hospitalization despite antibiotics. Based on literature, there will be no added risk of infection whether a patient is given antibiotics or not.

The most common side effect of antibiotic administration (Cefoxitin) is Diarrhea. Other rare side effects seen in less than 1% of patients given this drug includes Anemia, or decrease in hemoglobin, Increase in eosinophils in the blood, elevated liver enzymes, Decrease in platelets, and decrease in white blood cells. Patients who have allergies to antibiotics may also experience hypersensitivity reactions to this drug. There is also risk of alteration of the normal bacterial flora, which promotes antimicrobial resistance. This will decrease susceptibility of bacteria to antimicrobials making infections harder to treat.

Benefits

You will not receive direct benefits by participating in this study, however you may be spared from potential side effects of antibiotics. Furthermore, future prostate biopsy patients will benefit from enhanced guidelines on the need for prophylactic antibiotics to balance the risk of infection versus occurrence for antibiotic resistance.

Criteria for withdrawing subjects from the study and stopping the study as a whole

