Patients experiencing an adverse event such as symptoms of urinary tract infection like hematuria, dysuria, frequency, and urgency and systemic symptoms such as fever, generalized weakness, malaise will be evaluated right away initially with a complete blood count, urinalysis, and urine culture. Patients who will satisfy the criteria of Urinary Tract Infection, will be considered as having post biopsy infectious complications, and will be evaluated for possible sepsis. According to literature, 2% of patients undergoing prostate biopsy may experience mild post biopsy infection. 1% of patients may develop severe infections or urosepsis requiring hospitalization²². Computed sample size for the study is a total of 120 patients, with 60 patients in each arm. Hence, if more than 2 patients develop mild biopsy infection, and more than 1 patient develop severe infections from the experimental group, the study will be terminated and conclusion will be recommendation of administration of antibiotic prophylaxis. Patients who were not able to complete the procedure due to any circumstance, those who cannot tolerate anesthesia, those with adverse effects from anesthesia or antibiotics, and patients not compliant to follow up tests will be withdrawn from the study.

Data to be gathered

Patients who will pass the inclusion criteria will have their demographic data recorded such as age, sex, Height, Weight, BMI, Charlson Scores, Prostate volume, PSA, and History of Previous Biopsies. Post operatively, UTI will be assessed using a symptom checklist, which includes dysuria, urgency, frequency, or hematuria, fever, flank pain, nausea/vomiting. Signs of Systemic Inflammatory Response Syndrome (SIRS) will be gathered in patients who develop signs of urinary tract infection, namely, Temperature, Heart Rate, Respiratory Rate, White Blood Cell Count, and Blood Pressure. Incidence of sepsis and UTI In both groups will be recorded. Patients with Fever, or 2 or more signs of SIRS will be advised admission immediately. Histopathology results, 30 day readmissions, 30 day emergency room visit, and non infectious complications based on the Clavien Dindo classification will also be gathered.

Laboratory/assessment procedures to be performed

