All patients will be followed for 30 days for and assessed for post procedure infection. Initial assessment will be at 7 days post operatively with a history and physical exam. Symptoms of Urinary tract infection will be recorded. Urinalysis and urine culture will also be taken this time. Patients who are asymptomatic will be followed for 30 days, and will be asked to report symptoms of infection. All events within 30 days such as hospital admissions, emergency room visits, and non-infectious complications such as acute urinary retention will be reported. Mild and self limiting lower urinary tract symptoms, and hematuria will not be recorded as urinary tract infection as these are commonly seen after prostate biopsy. Patients who remain asymptomatic after the 30th post operative day will be treated as not having a post procedural infection. Persistent and severe lower urinary tract symptoms with associated fever will be assessed as having developed a post procedural infection, and patients will be treated accordingly. For patients who report symptoms on initial assessment, or within the 30 day time period, patients will be asked to contact primary investigator immediately for assessment, and will be asked to do a baseline Complete Blood Count, Urinalysis, and Urine Culture. Patients with mild to moderate illness (symptoms of fever and lower urinary tract symptoms such as those mentioned above, without urosepsis, circulatory failure and/or organ dysfunction may be treated as outpatient. Patients will be started on Ciprofloxacin 500mg 2x a day for 4 weeks, in line with recommendations of the European Association of Urology on treating Acute Prostatitis. Patients with marked debility and signs of sepsis as mentioned above, patients in whom there is uncertainty in diagnosis, and patients in whom there is concern about adherence to treatment, or patients unable to maintain oral hydration, or take oral medications, are patients in whom hospitalization will be advised. Baseline Complete Blood Count, Creatinine, Urinalysis, Urine Culture and Sensitivity and additional Blood culture and sensitivity will be done. Patients will be admitted in the private room of the hospital, and will be started on Broad Spectrum Antibiotics. Other additional medical management may vary depending on signs, symptoms and culture results. Hospital stay may vary as well, depending on signs and symptoms.

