A minimum sample of 60 patients per group is needed for a non-inferiority study with binary outcomes. Basourakos, et al reported that rates of post-biopsy genitourinary infections were 1.35% in the AP group and 1.22% in the NAP group²⁴. The target set was at least 80% power and 90% confidence interval. This was computed using Sealed Envelope Ltd. 2012. Power calculator for binary outcome non-inferiority trial. There are paucity of data regarding post prostate biopsy infections in patients without antibiotic prophylaxis. Similarly, data on post biopsy infections in Filipinos are lacking. A study reported by Yaddao, et al., published in the Philippine Journal of Urology, reported an infection rate of 5% occurring after biopsy, hence, we chose 5% as our non-inferiority limit.

Data Analysis

To assess the primary and secondary outcomes, we analyzed the 90% confidence interval (CI) of the difference in proportions, following Altman's recommendation. Non-inferiority was established if the upper bound of the 90% CI was less than 5%. Descriptive statistics, including median, percentages, 90% CI, or interquartile range (IQR), were reported as appropriate. For comparisons between groups, an independent t-test was used for continuous variables, while the chi-square or Fisher's exact test was applied for categorical variables. All statistical calculations were performed using MedCalc Statistical Software version 23.2.6

Ethical Considerations

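### Withdrawing randomised patients for antibiotic side effects or missed follow-up tests conflicts with the 30-day follow-up rule and can bias a comparison that one infection may decide

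*Protocol*

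**What the plan says.** Randomisation and Blinding procedures places allocation before the syringe and the biopsy: "Once the patient has given his signed consent, and patient is eligible to join the study, he will then be randomized". Under the description of study groups, "In the experimental group, patients will be given normal saline solution in a syringe", while Group B receives cefoxitin.

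The section on withdrawing subjects and stopping the study then lists reasons for removal. Besides uncompleted procedures and intolerance of anaesthesia, "those with adverse effects from anesthesia or antibiotics, and patients not compliant to follow up tests will be withdrawn from the study". The tests concerned are the urinalysis and urine culture at 7 days, which Laboratory/assessment procedures makes the laboratory part of the infection assessment.

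Follow-up procedures says something different. It has all patients followed for 30 days and assessed for infection, adds that "Patients who are asymptomatic will be followed for 30 days, and will be asked to report symptoms of infection", and has patients with adverse effects followed until these resolve or stabilise.

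On size, Sample Size and Sampling Technique states: "A minimum sample of 60 patients per group is needed for a non-inferiority study with binary outcomes". The withdrawal section plans exactly 120 in total. No allowance for losses is stated. Data Analysis sets success as an upper 90% limit for the difference in proportions below 5%. It cites a recommendation for the interval without writing out the formula.

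**The concern.** Both reasons act after allocation, and neither is neutral.

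- **Antibiotic adverse effects.** For the prophylactic drug these can arise only in Group B. Under Benefits, patients are told "however you may be spared from potential side effects of antibiotics", yet those who show such effects are the ones to be withdrawn. The wording is also not limited to the prophylactic dose. Infected patients in either arm are treated with antibiotics, so read literally it could cover someone who has already had the primary event.
- **Missed tests.** A patient who feels ill, or who is being treated elsewhere, may be the one who does not return for the day-7 urinalysis and culture.

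If follow-up stops at withdrawal, later infections go unrecorded and no analysis can recover them. If the patient also leaves the denominator, the groups compared are no longer those that were randomised. With so few events expected, the non-inferiority conclusion could turn on one such patient.

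**Working it through.** **Inputs (Protocol).** 60 per arm; infection rates 1.22% without prophylaxis (A) and 1.35% with it (B); margin 5 percentage points; 80% power; 90% interval, so z = 1.645 and z² = 2.706. The rates, margin and confidence level are in Sample Size and Sampling Technique; the success rule is in Data Analysis.

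**Assumption.** The interval formula is not given, so Newcombe (built from Wilson limits) and Wald are both shown.

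**1. The plan's own figure.**
n = (1.645 + 0.842)² × [0.0122×0.9878 + 0.0135×0.9865] / (0.05 + 0.0135 − 0.0122)²
= 6.18 × 0.02537 / 0.002632 = 59.6, rounded up to 60.
The stated size reproduces, and it is the bare formula result with nothing added for losses.

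**2. Expected infections.** A: 60 × 0.0122 = 0.73. B: 60 × 0.0135 = 0.81.

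**3. Effect of one patient on the upper limit for A minus B.**
Newcombe: d + √[(uA − pA)² + (pB − lB)²], where d = pA − pB, uA is the Wilson upper limit in A and lB the Wilson lower limit in B.
Wald: d + 1.645 × √[pA(1−pA)/nA + pB(1−pB)/nB].

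For 1/60 v 0/60 the B term is zero, so the Newcombe limit is the Wilson upper limit for 1/60, 7.13%. For 0/59 v 0/60 it is 2.706/(59 + 2.706) = 4.38%.

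| Recorded infections, A v B | Newcombe | Wald |
|---|---|---|
| 1/60 v 0/60 | 7.13% fail | 4.39% pass |
| same, A case removed: 0/59 v 0/60 | 4.38% pass | zero width |
| 1/60 v 1/60 | 5.62% fail | 3.84% pass |
| same, A case removed: 0/59 v 1/60 | 2.90% pass | 1.05% pass |
| 2/60 v 0/60 | 9.58% fail | 7.15% fail |
| same, A case removed: 1/59 v 0/60 | 7.25% fail | 4.46% pass |

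The counts at which the result reverses differ by method, but each method has a one-patient reversal close to the expected counts. Removing a Group B case can act the other way: under Newcombe, 1/60 v 2/60 passes (4.23%) and 1/60 v 1/59 fails (5.59%).

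**4. Losses without any event (conditional illustration).** With zero infections in both arms the Newcombe limit is z²/(nA + z²). It is below 0.05 only if nA > 19 × 2.706 = 51.4, so Group A needs at least 52 analysed patients (4.95% at 52, 5.04% at 51).

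**The case against.** **Exclusion from analysis is not stated.** The text says withdrawn from the study, and analysis sets are commonly left to a statistical analysis plan, which is not at hand. This stands, so the numerical consequences are conditional. It does not remove the contradiction with Follow-up procedures. Nor could a later plan restore outcomes that were never collected.

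**A detected infection is unlikely to be lost.** Symptomatic patients are evaluated at once, those meeting the criteria are counted as infectious complications, and infection is not itself a withdrawal reason. Ethical Considerations adds teleconsults at 24 and 48 hours and a visit within 14 days. This also stands. The plausible route is narrower: an infection not yet recorded in a patient who misses the tests or is cared for elsewhere.

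**Adverse effects are still monitored.** They are, and non-infectious complications are graded. Withdrawal need not erase those records, but antibiotic side effects are not among the listed outcomes. Because treatment is blinded, a reaction attributed to an antibiotic could also lead to withdrawal after saline, so this reason acts mainly rather than solely on Group B.

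**A stronger reading.** A reader might infer that withdrawals could shrink Group A until non-inferiority is unattainable. The document does not support that. Side effects of the prophylactic drug deplete Group B, not Group A. The floor of 52 applies only with no event in either arm under Newcombe: 0/51 v 1/60 passes at 3.53%, and Wald has no floor. Falling to 51 would take 9 losses (15%) in Group A, and the protocol gives no loss rate that makes this likely.

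**Conclusion.** The point holds as a contradiction and a source of bias. The withdrawal rule acts after randomisation, is partly tied to arm and possibly to outcome, and conflicts with the statements that all patients are followed for 30 days and that adverse effects are followed to resolution. If withdrawn patients leave follow-up or the denominator, which is the natural but unstated reading, one unrecorded Group A infection can move the upper limit across the 5% margin: from 7.13% to 4.38% under Newcombe, or from 7.15% to 4.46% under Wald. Neither the interval method nor the frequency of withdrawal is given, so this shows how fragile the result is and does not forecast it. The sample size has no reserve, but that is secondary. The point does not claim that success becomes impossible.

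**What to change.** 1. Reconcile the withdrawal section with Follow-up procedures, so that adverse effects and missed tests are not reasons to leave follow-up or analysis. Decisions about an individual's treatment are a separate clinical matter and are not affected.
2. State that every randomised patient who was biopsied stays in the primary analysis in the assigned group. Report those not biopsied by arm and reason.
3. For patients who miss the day-7 tests, establish 30-day infection status by phone, using the existing symptom checklist, and by chart review. The teleconsult route in Ethical Considerations can carry this.
4. Record antibiotic adverse effects as an outcome by arm.
5. Report the compliant-only set as a second analysis, with a worst-case count for patients whose status stays unknown.

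The cost is a change of wording, a few phone calls and one extra table. If some losses are still expected, the reserve should be stated. For example, an assumed 10% loss would need 60/0.90 = 66.7, so 67 per arm. The protocol gives no loss rate, so that percentage is illustrative.

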Chronic Bacterial Prostatitis is a bacterial infection of the prostate lasting more than 3 months. Urine cultures are persistently positive for the same organism. E. coli is still the most common organism isolated. Patients present with recurrent or relapsing urinary tract infections, urethritis, or epididymitis with the same bacterial strain. Diagnosis is made through history or physical examination, Voiding test such as pre and post prostatic massage and a positive urine culture²⁸.

Asymptomatic prostatitis is diagnosed when inflammatory cells are identified incidentally on prostate biopsy on an asymptomatic patient. Treatment is catered based on the primary reason for urologic consultation. Further urologic evaluation is indicated if the reason for consult is an increased PSA²⁸.

Preoperative antibiotic prophylaxis is the administration of antibiotics before surgery to reduce the risk of post operative infection. Although the timing of antibiotic administration varies, the goal of preoperative systemic antibiotic prophylaxis is to maintain the highest tissue concentrations at baseline and during surgery. The literature recommends at least 30 minutes and no more than 60 minutes before skin incision to achieve the optimal time for preoperative administration of the most commonly used antibiotics²⁹.

Post biopsy infection is the Occurrence of Lower Urinary tract Infection symptoms such as frequency, dysuria, and urgency, or Severe Urinary Tract Infection such as loin pain, rigour and fever³. Microbiologic tests include a positive urinalysis, and urine culture. Occurrence of urosepsis, meeting a SOFA score of > 2 in the presence of a urinary tract pathogen, all of which occurring within 2 weeks post biopsy.

Objectives

General Objective

To compare incidence infectious complications in patients given antibiotic prophylaxis versus no prophylaxis among patients at St. Luke's Medical Center Global City and Quezon City from March 2024- January 2024

Specific Objective

- 1. To compare the incidence of urinary tract infection and sepsis between patients without and with antibiotic prophylaxis undergoing prostate biopsy.
- 2. To compare Hospital admissions, Emergency room visits, and non-infectious complications between the no prophylaxis versus prophylaxis groups.

Methods

Study design and setting

This will be a randomized controlled trial to be conducted at St. Luke's Medical Center Global City and Quezon City from June 2024 to June 2025.

Study population

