The study population will include patients indicated to undergo prostate biopsy as part of Prostate Cancer Diagnosis.

Criteria for Subject Selection Inclusion Criteria

- 1. Age 40-75 years.
- 2. American Society of Anesthesiologists score of I or II
- 3. Those undergoing Transperineal Prostate Biopsy
- 4. Urinalysis Negative Patients
- 5. Non Tender Prostate on DRE
- 6. Asymptomatic Patients
- 7. Charlson Score <5

Exclusion Criteria

- 1. Acute prostatitis within the last 6 months.
- 2. History of documented Urinary Tract Infection (UTI), or symptoms of UTI (painful micturition, Frequency, Urgence, suprapubic or flank pain, cloudy and foul-smelling urine) for the past 6 months.
- 3. Tender and boggy prostate on initial DRE
- 4. With ongoing antibiotics treatment for the past month
- 5. History of antibiotic allergy
- 6. Prior definitive therapy for prostate cancer, such as radiation therapy or partial gland ablation.
- 7. Those with uncontrolled diabetes mellitus, immunocompromised or immunosuppressed status.
- 8. Those with other pre-existing urinary tract conditions such as Benign Prostatic Hyperplasia in retention, Urinary retention from neurogenic causes, and those with indwelling stents or urethral catheters
- 9. Those with Prosthetic Heart Valves
- 10. Patients with ongoing infection elsewhere
- 11. Patients with Bleeding Disorders
- 12. Patients with Asymptomatic Bacteriuria

Description of Study Procedure

Method of subject selection and recruitment

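### Withdrawing patients for antibiotic adverse effects removes randomised patients selectively from the cefoxitin arm and conflicts with the 30-day follow-up of all patients

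*Protocol*

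**What the plan says.** The Protocol section on criteria for withdrawing subjects lists several kinds of patient in one sentence. It starts with those who do not complete the procedure for whatever reason and those who cannot tolerate anesthesia, and it ends: "those with adverse effects from anesthesia or antibiotics, and patients not compliant to follow up tests will be withdrawn from the study". Withdrawal is from the study, not just from dosing, and no severity threshold or time window is given.

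Patients are randomised after consent and eligibility (Randomization and Blinding procedures). Dosing comes later. Group A receives saline; for Group B, "Patients will be given 2g IV of Cefoxitin 1 hour prior to the procedure".

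Follow-up procedures says: "All patients will be followed for 30 days for and assessed for post procedure infection". It adds: "All events within 30 days such as hospital admissions, emergency room visits, and non-infectious complications such as acute urinary retention will be reported". The same section follows patients with adverse effects until these resolve or stabilise, and Ethical Considerations adds teleconsults at 24 and 48 hours.

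The second specific objective is "To compare Hospital admissions, Emergency room visits, and non-infectious complications between the no prophylaxis versus prophylaxis groups". Under Data to be gathered, "non infectious complications based on the Clavien Dindo classification will also be gathered". The only named example of such a complication is acute urinary retention, and it is given as an example, not as a closed list. Data Analysis assesses primary and secondary outcomes by a 90% confidence interval for the difference in proportions.

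**The concern.** The trigger arises after randomisation and depends on the treatment received. The anesthesia part of the sentence applies to both arms alike. The antibiotic part does not, because a true reaction to the study antibiotic cannot occur in a patient given saline. Comparing arms after a withdrawal of this kind no longer compares the groups as randomised.

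Site staff also cannot fully obey both instructions: withdraw the patient from the study, and follow every patient for 30 days with all events reported. If they follow the first, a withdrawn Group B patient's later admission, emergency visit or complication may never be collected, and no analysis plan can restore it.

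At stake is the secondary comparison of non-infectious complications. Sparing patients the side effects of antibiotics is a benefit the Protocol itself cites (Benefits), so this is where some of the evidence for that benefit would appear.

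**Working it through.** **The plan's own figure.** The Protocol gives 60 per group: rates 1.35% with and 1.22% without prophylaxis, margin 5%, 80% power, 90% interval (one-sided 0.05).

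- n = (1.645 + 0.842)² × (0.0135 × 0.9865 + 0.0122 × 0.9878) / (0.05 + 0.0013)² = 59.6, rounded up to 60. The figure reproduces.
- With 60 in Group A and fewer in Group B, power = Φ(0.0513/SE − 1.645), where SE = √(0.0135 × 0.9865/n_B + 0.0122 × 0.9878/60). For n_B = 60 this is 80.2%; for n_B = 57 it is 79.3%. Power is not the issue.

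**How many patients could be withdrawn.** The Protocol gives no overall cefoxitin reaction rate. Risks names diarrhea as the most common effect, without a rate, and then: "Other rare side effects seen in less than 1% of patients given this drug". I therefore assume 1% to 5%.

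- Expected number in Group B: 60 × 0.01 = 0.6; 60 × 0.05 = 3.
- Chance that nobody is affected: 0.99^60 = 55%; 0.95^60 = 5%.

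**Effect on the Group B complication rate.** Let k be the number withdrawn for a reaction and x the number of other complications among Group B patients who stay in. I assume x = 0 to 4.

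1. *Withdrawn patients and their events are kept in the analysis.* No under-count.
2. *They are left out, and reactions count as complications.* The fall in the rate is (x + k)/60 − x/(60 − k):

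| | x = 0 | x = 2 | x = 4 |
|---|---|---|---|
| k = 1 | 1.67 points | 1.61 | 1.55 |
| k = 3 | 5.00 points | 4.82 | 4.65 |

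That is 1.55 to 1.67 points per lost reaction.

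3. *They are left out, and reactions do not count.* Only the denominator shrinks, and the rate rises by x/(60 − k) − x/60. This is 0 for x = 0 and 4/57 − 4/60 = 0.35 points for x = 4, k = 3. It assumes that no withdrawn patient has another complication. If one does and it is lost, the rate falls instead: with four complications in all, one of them in a single withdrawn patient, 4/60 − 3/59 = 1.58 points.

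**In expectation.** With an assumed 2% background rate in both arms and reactions counted, the true Group B rate is 1 − 0.98 × (1 − reaction rate): 3.0% at a 1% reaction rate and 6.9% at 5%. With reacting patients removed, it would read 2.0%, the same as Group A.

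**The case against.** The case on the other side is substantial.

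- *Handling of withdrawals may be in an analysis plan.* The Protocol does not say that withdrawn patients leave the analysis, and a plan not at hand may keep them. This stands: the under-count is conditional. It does not cover later events that sites stop collecting.
- *The reaction itself is already known.* It is what triggers the withdrawal, so whether to count it can still be decided at analysis. This stands. Only events after withdrawal are beyond recovery.
- *Other text points towards capture.* Follow-up of adverse effects to resolution concerns exactly these patients. This stands in part. It is a safety provision that neither cancels the withdrawal rule nor places the patient in the numerator or denominator of the comparison.
- *Few reactions would qualify.* "History of antibiotic allergy" is an exclusion criterion. The listed rare effects are largely laboratory findings, whereas the scheduled post-biopsy tests are urinalysis and urine culture. Nothing shows that diarrhea after a single dose was meant to count. This stands and keeps the likely size small; serious reactions may also surface as emergency visits or admissions.
- *The clause may be meant only for the time around the procedure.* Its neighbours suggest so. But it sets no window, and a patient who reacts before biopsy has already been randomised.
- *Blinding spreads suspected reactions over both arms.* True, and if the word antibiotics also covered treatment with ciprofloxacin, Group A patients could trigger the rule. The natural reading is the study prophylaxis, and the excess of true reactions remains in Group B.

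**Conclusion.** The point holds as a fault in the withdrawal rule. The Protocol states a treatment-dependent withdrawal after randomisation, in conflict with its own 30-day follow-up of all patients. As written, it removes Group B patients selectively and can lose their later events. Bias in the non-infectious complication comparison follows only under further conditions that the Protocol neither states nor rules out. The size is probably small: 0.6 to 3 of 60 patients, resting on assumed reaction rates of 1% to 5% and 0 to 4 other complications.

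Three stronger readings are tempting, and the document does not support them.

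- A reader might infer that withdrawn patients are dropped from the analysis. No passage says so.
- A reader might infer that the error can only work against omitting prophylaxis. The direction depends on whether reactions count. If they do, Group B's rate is understated and prophylaxis looks safer than it is. If they do not, the smaller denominator may raise Group B's rate by up to about 0.4 points, which slightly favours omission.
- A reader might infer that the infection comparison is compromised. I make no such claim. Even with 3 patients lost, at the planning rate of 1.35% the expected number of missed infections is 3 × 0.0135 = 0.04.

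**What to change.** In the withdrawal criteria, make antibiotic adverse effects grounds for stopping the study injection or the biopsy, not for leaving the study. Suggested wording:

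*Patients with adverse effects from the study injection, including those whose biopsy is stopped for this reason, stay in 30-day follow-up and are analysed in their randomised group; the reaction is recorded and graded by Clavien-Dindo with the other non-infectious complications.*

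The clause that withdraws anyone who does not complete the procedure, for whatever reason, must be made subject to this exception. Otherwise a patient whose biopsy is stopped by a reaction is still withdrawn under it. The wording also settles, on purpose, that drug reactions belong to the non-infectious complications, which the Protocol leaves open.

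Cost: one or two sentences and slight analysis work, with no new visit, test or patients. The downside is that a few patients without a completed biopsy stay in the analysis, and the secondary estimate remains imprecise at 60 per arm.
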